Statistical Analysis Plan (Final, Version 1.2)

Principal Investigator: [name]

Research Institution: Sir Run Run Shaw Hospital, Zhejiang University

Register Number: NCT06204497

Date: 2025-10-26

Version: 1.2

Statistical Analysis Plan Authors: [name]

Department of Epidemiology and Biostatistics, Zhejiang University

School of Medicine, China

E-mail: [contact]

1. Introduction

This trial is a multicenter, prospective, randomized, controlled, open label, parallel-group, non-inferiority trial to evaluate the safety and efficacy of stent-based diverting technique (SDT) versus ileostomy in rectal cancer patients. In this trial, SDT is considered to reduce the overall length of post-operation hospital stay and medical costs, improve patients' quality of life, while not increasing the peri-operative complication rate. The primary outcome was the 90-day incidence of severe complications (Clavien-Dindo grade \geq III). Secondary outcomes included overall complication rate, anastomotic leakage rate (grade B/C), length of postoperative hospital stay, hospitalization costs, and 90-day postoperative quality of life.

Patients were randomized 1:1 to two groups:

- SDT group: rectal cancer surgery plus stent-based diverting technique
- Ileostomy group: rectal cancer surgery plus protective ileostomy

Follow-up concluded 90 days after the last patient underwent surgery.

2. Population

● 2.1 Intent-to-treat population

The intent-to-treat (ITT) population will include all randomized participants, with grouping according to their originally assigned treatment,

regardless of whether the allocated intervention was actually received or completed. Primary and secondary outcome analyses will be performed in the intent-to-treat (ITT) population. As randomization was performed intraoperatively, a modified ITT (mITT) population was not defined in this study.

- **2.2 Per-protocol population**

The per-protocol (PP) population includes all randomized participants who completed the study as planned, with no major protocol violations, adequate adherence to the assigned intervention, and sufficient follow-up data for the primary outcome assessment. Primary and secondary outcome analyses will be conducted in the PP population as sensitivity analyses.

- **2.3 As-treated population**

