4.6 Primary outcome

The primary endpoint will be analyzed in the ITT population and defined as the rate of severe complications (Clavien-Dindo grade \geq III) within 90 days post-surgery, the primary endpoint will be assessed as follows (Time Frame: For the Study Group, from the SDT to 90 days after surgery; if the patient undergoes ileostomy as a salvage procedure, the time frame will be extended to 90 days after stoma reversal. For the Control Group, from ileostomy creation to 90 days after stoma reversal. For patients in

both groups who do not undergo stoma reversal, the time frame will be defined as 90 days after the initial surgery).

The primary non-inferiority analysis will be based on the risk difference (RD) with a predefined non-inferiority margin of 2.8%. The RD and its 97.5% one-sided confidence interval will be estimated using binomial regression with identity link. For the relative risk (RR), binomial regression with log link will be used to estimate the RR and two-sided 95% confidence interval. The RR is reported as a supplementary effect measure and will not be used for the non-inferiority test ((see appendix Table 2).

Non-inferiority margin justification: The non-inferiority margin of 2.8% was determined based on clinical relevance and pilot data. This margin was defined such that the severe complication rate in the SDT group would not exceed 120% of that in the ileostomy group (i.e., a 20% relative increase). Given the expected severe complication rate of 14% in the ileostomy group in our pilot study, the absolute non-inferiority margin was calculated as $14\% \times 0.2 = 2.8\%$. In clinical practice, an absolute increase of no more than 2.8% in severe complications is considered acceptable, as it is negligible compared with the substantial benefits of SDT: avoidance of stoma creation and reversal, shorter hospital stay, lower medical costs, and improved quality of life.

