Number of high-risk factors, No. (%)		
Single	XX (XX)	XX (XX)
Multiple	XX (XX)	XX (XX)
Pathological TNM stage, No. (%)		
0	XX (XX)	XX (XX)
I	XX (XX)	XX (XX)
II	XX (XX)	XX (XX)
III	XX (XX)	XX (XX)

Table 2

Outcomes	Stent-based Diverting Technique (n=)	Ileostomy (n=)	P value
Primary outcome			
Events (severe complications), No	XX	XX	
Incidence of severe complications, % (95% CI)*	XX (95% CI, XX– XX)	XX (95% CI, XX– XX)	
Between-group difference in incidence, % (97.5% CI)	-XX (–∞, XX%)	-	XX
Relative ratio, % (95% CI)*	XX (XX–XX)	-	XX
Secondary outcomes			
Incidence of total complications, No. (%)*	XX (XX)	XX (XX)	XX
Incidence of mild complications, No. (%)*	XX (XX)	XX (XX)	XX
Complications (Events)	XX (XX)	XX (XX)	-
General complications, No. (%)	XX (XX)	XX (XX)	-
Anastomotic leakage (Grade B)	XX (XX)	XX (XX)	XX
Anastomotic leakage (Grade C)	XX (XX)	XX (XX)	XX
Anastomotic stenosis	XX (XX)	XX (XX)	XX
Intestinal obstruction	XX (XX)	XX (XX)	XX
Intestinal perforation	XX (XX)	XX (XX)	XX
Abdominal infection	XX (XX)	XX (XX)	XX
Bleeding	XX (XX)	XX (XX)	XX
Others†	XX (XX)	XX (XX)	XX
Stent or Tube-related complications, No. (%)	XX (XX)	XX (XX)	-
Stent displacement	XX (XX)	XX (XX)	-
Intestinal fistula‡	XX (XX)	XX (XX)	-
Mushroom-shaped tube-related dermatitis	XX (XX)	XX (XX)	-
Mushroom-shaped tube displacement	XX (XX)	XX (XX)	-
Stoma-related complications, No. (%)	XX (XX)	XX (XX)	-

Parastomal hernia	XX (XX)	XX (XX)	-
Dermatitis	XX (XX)	XX (XX)	-
Stoma obstruction	XX (XX)	XX (XX)	-
Stoma bleeding	XX (XX)	XX (XX)	-
Grade of complications			
I	XX (XX)	XX (XX)	XX
II	XX (XX)	XX (XX)	XX
III	XX (XX)	XX (XX)	XX
IV	XX (XX)	XX (XX)	XX
V§	XX (XX)	XX (XX)	XX
Converse to Stent-based Diverting Technique, No. (%)	-	XX (XX)	-
Converse to ileostomy, No. (%)	XX (XX)	-	-
Converse to salvage ileostomy, No. (%)	XX (XX)	-	-
Time of stent degradation			
No stent	XX (XX)	XX (XX)	-
Stent displacement	XX (XX)	XX (XX)	-
Before 3 weeks	XX (XX)	XX (XX)	-
3-4 weeks	XX (XX)	XX (XX)	-
5-6 weeks	XX (XX)	XX (XX)	-
Stoma ending, No. (%)#			
No stoma	XX (XX)	XX (XX)	-
Reversal on time (stage II)	XX (XX)	XX (XX)	-
Delayed reversal	XX (XX)	XX (XX)	-

Table 3

	Stent-based Diverting Technique	Ileostomy	P value
PHS and Costs	n=	n=	
Unplanned readmission, No. (%)	XX ± XX	XX ± XX	XX
PHS (stage I), days	XX ± XX	XX ± XX	XX
PHS (stage II), days	XX ± XX	XX ± XX	XX
PHS (Readmission),	XX ± XX	XX ± XX	XX
Total PHS, days*	XX ± XX	XX ± XX	XX
Total PHS (Only patients with reversal), days*	XX ± XX	XX ± XX	XX

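### The '90-day' primary endpoint uses windows that differ by arm and by later events; the SAP states no strategy estimand and plans no common-window analysis

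*SAP*

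**What the plan says.** Section 1 of the SAP (Version 1.2) states: "The primary outcome was the 90-day incidence of severe complications". Section 4.6 repeats the 90-day description and then qualifies it in the same sentence: "within 90 days post-surgery, the primary endpoint will be assessed as follows". Four branches follow:

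- **SDT, default:** "For the Study Group, from the SDT to 90 days after surgery".
- **SDT after salvage:** "if the patient undergoes ileostomy as a salvage procedure, the time frame will be extended to 90 days after stoma reversal".
- **Control:** "For the Control Group, from ileostomy creation to 90 days after stoma reversal". No upper limit is put on the interval to reversal.
- **No reversal, either arm:** for patients in "both groups who do not undergo stoma reversal, the time frame will be defined as 90 days after the initial surgery".

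The test is a risk difference from an identity-link binomial regression, with a one-sided 97.5% interval and a 2.8% margin. Nothing in it allows for time at risk. Section 4.8 repeats the analysis in the per-protocol and as-treated populations, so it varies who is analysed and not the period counted.

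On closing the study, section 1 says: "Follow-up concluded 90 days after the last patient underwent surgery". It does not say which surgery. Section 4.1 places database lock after every patient's 90-day follow-up.

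**The concern.** Three features of the only confirmatory comparison do not fit together.

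1. **Label.** A reader told that a 90-day rate was non-inferior will assume 90 days in both arms. For every reversed control the period is the time to reversal plus 90 days, and it includes a second operation.
2. **Estimand.** Reversal belongs to the ileostomy strategy, so counting its complications can be justified, but the SAP never says that this is the comparison intended. The window also admits more than reversal complications. Appendix Table 2 lists general complications that can occur in either arm, such as stenosis, obstruction and leakage. After day 90 these count in a reversed control and not in an SDT patient without salvage. Reversal and salvage both happen after randomisation, so later events set the length of the window.
3. **Closing rule.** A control window that ends 90 days after reversal may not be complete at a cut-off set 90 days after an unspecified surgery.

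The interpretation of a non-inferiority claim is at stake. Without a common-window analysis, nobody can tell whether a favourable risk difference reflects avoided reversal complications or a shorter counting period for SDT.

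**Working it through.** **The plan's own figure.** Section 4.6 gives a 14% control rate and a 20% relative increase: 0.14 × 0.20 = 0.028. The 2.8% margin reproduces, and the implied SDT ceiling is 14% + 2.8% = 16.8%. The SAP does not say which window the pilot 14% refers to.

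**What the unequal windows do.** Let s and c be the shares of SDT and control patients with a severe event by day 90 after index surgery. Let x be the share of controls whose first severe event falls after day 90 but inside their window. Let y be the share of SDT patients whose first severe event falls in the same later period and is not counted. The salvage extension is left aside.

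- SAP risk difference = s − (c + x)
- Day-90-from-index difference = s − c = SAP difference + x
- Equal long-window difference = (s + y) − (c + x) = SAP difference + y

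So x is the gap to a day-90 comparison and includes the defensible reversal burden. The gap to an equal long window is y alone. The SAP gives neither.

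**Illustration against day 90 from index.** Assume that the 14% refers to the long window and that x points of it arise only after day 90. The day-90 control rate is then 14 − x, and the tolerated excess is 16.8 − (14 − x) = 2.8 + x.

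| x (points) | Control rate to day 90 | Tolerated excess (points) | Relative increase |
|---|---|---|---|
| 0 | 14% | 2.8 | 20% |
| 1 | 13% | 3.8 | 29% |
| 2 | 12% | 4.8 | 40% |
| 3 | 11% | 5.8 | 53% |

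Now suppose SDT is truly worse by exactly 2.8 points to day 90. The chance that the SAP's test declares non-inferiority is Φ((0.028 − RD)/SE − 1.96), with RD = 0.028 − x and an unpooled SE. The SAP states no sample size, so n per arm is assumed. For x = 2 points and n = 500:

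- SDT rate 12% + 2.8% = 14.8%; control rate 14%; RD = 0.008
- SE = √(0.148×0.852/500 + 0.14×0.86/500) = 0.0222
- (0.028 − 0.008)/0.0222 − 1.96 = −1.06, so the probability is 14.5%

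| x (points) | n = 300 | n = 500 | n = 1000 |
|---|---|---|---|
| 0 | 2.5% | 2.5% | 2.5% |
| 1 | 5.3% | 6.5% | 9.1% |
| 2 | 10.3% | 14.5% | 24.6% |
| 3 | 18.5% | 27.8% | 49.2% |

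These are error rates for a day-90 claim only, not for a strategy claim.

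**Closing rule, if it means index surgery.** Assume uniform accrual over T = 18–30 months, reversal at R = 3–6 months, and cut-off 3 months after the last index operation.

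- Controls not yet reversed at cut-off: (R − 3)/T, from 0 (R = 3) to 3/18 = 17% (R = 6, T = 18).
- Controls without a full 90 days after reversal, including those not yet reversed: R/T, from 3/30 = 10% to 6/18 = 33%. Those already reversed are partly observed.

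Missing control events would lower the control rate. That works against SDT, the opposite direction to x.

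**The case against.** The best defence is that this is a comparison of strategies. Ileostomy commits the patient to a second operation, and stopping the control clock before it would hide a real cost. That stands. It means x cannot be read as bias throughout, and the false-claim rates above apply only to a day-90 benchmark. Several stronger readings fail for this and related reasons:

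- **That SDT could pass while being worse over any common period.** In a common window long enough to contain reversal, control reversal events count too. The conclusion would change only if late SDT events (y) were numerous, and the documents give no rate for them.
- **That the endpoint is 90 days only for SDT.** Unreversed controls also have 90 days, and SDT patients with salvage ileostomy have longer.
- **That unreversed controls escape being counted because complications prevented reversal.** The SAP gives no reasons for non-reversal, and a severe event by day 90 already counts in a yes/no endpoint.
- **That late controls will be scored as complete 90-day records.** The SAP does not say so. The appended, superseded Version 1.1 ended follow-up after the last patient's final surgery, and the amendment summary lists no change to this. That supports a benign reading. The current wording still leaves it open, and the no-reversal branch would fit such patients unless the plan says otherwise.
- **That the missing unreversed category under stoma outcome in Table 2 proves the point.** That row carries a footnote mark whose text is not available.

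It is also fair to object to a second mandatory non-inferiority hurdle. It would change the success rule of a final plan and reuse a margin built on a 14% rate whose window is unknown. The fix therefore asks for a sensitivity analysis.

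**Conclusion.** The point holds in limited form. The 90-day label does not describe the windows in section 4.6. The strategy comparison that would justify them is not stated, and no planned analysis tests them. This bears on the trial's only confirmatory comparison and on what a non-inferiority claim may be said to show.

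The size cannot be derived from the SAP. Relative to a day-90-from-index comparison, the tolerated excess grows one for one with x, for example to 4.8 points if x is 2. Part of that is reversal burden properly charged to ileostomy. The part that is hard to defend, late SDT events left uncounted, cannot be quantified from the document. If the closing rule refers to index surgery, about 0–17% of controls would be unreversed at cut-off under the assumed timings. If it refers to the final operation, the problem is one of wording.

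**What to change.** 1. **Label and estimand.** Drop the unqualified 90-day description in sections 1 and 4.6. State that the primary contrast compares treatment strategies over the windows listed.
2. **Common-window analysis.** Add to section 4.8 the same risk difference with both arms counted to day 90 after index surgery, read against the 2.8% margin, with a note that the window of the pilot 14% should be stated. Every branch of section 4.6 already covers those 90 days. Report index-phase and reversal-phase events separately, and discuss any disagreement with the primary result when claiming non-inferiority. If SDT events after day 90 were collected, add an equal-length window that contains reversal plus 90 days.
3. **Closing rule.** Reconcile the follow-up end in section 1 and the lock rule in section 4.1 with the control window. Treat controls who are unreversed, or under 90 days from reversal, at cut-off as incomplete follow-up, and report their number.

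The additions should be made by dated amendment before results by arm are seen, or otherwise labelled as added afterwards. The cost is SAP wording and a little more analysis, provided that complications are recorded with dates, which the SAP does not confirm. The downside is a result that may look less favourable to SDT.

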4.2 General calculations

For the summary of population characteristics, all percentages will be calculated with the total number of the intent-to-treat (ITT) population as the denominator (including all patients with missing data for the relevant variable). For the summary of categorical outcome variables (e.g., complication rate), patients with missing data will be excluded from the denominator when calculating percentages. For the summary of continuous outcome variables (e.g., estimated blood loss, length of hospital stay, cost), patients with missing data will be excluded when calculating means or medians. When patients with missing data are excluded from the denominator, the number of patients included in the summary will be clearly reported.

All percentages, means, standard deviations (SDs), medians, interquartile ranges (IQRs), and ranges will be rounded to 2 decimal place. P-values will be rounded to 3 decimal places. Parameter estimates, standard errors (SEs), relative ratios (RRs), and 95% confidence intervals (CIs) will be reported to 2 decimal places. The primary outcome will be performed one-sided at $\alpha = 0.025$, with results presented as treatment differences and corresponding 97.5% one-sided confidence intervals. Other comparisons will be two-sided at $\alpha = 0.05$, with 95% two-sided confidence intervals reported.

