4.3 Missing data

For missing baseline data (age, BMI, etc.), multiple imputation by chained equations (MICE) will be used. The number of imputed datasets, imputation variables, and diagnostic checks will be fully documented. For quality of life (QoL) data with missing values, only observed cases will be included in the analysis (missing values excluded from denominator). For crossover or treatment-switching patients, the ITT principle will be strictly maintained in the primary analysis; treatment switching will be summarized descriptively and explored in the as-treated sensitivity analysis. For protocol deviations, all major violations will be listed by center and patient, with impact on the primary outcome assessed in PP and AT analyses.

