Subgroup analysis will be performed according to: Age (≥ 60 y or <60 y), Gender (female or male), Body mass index (≥ 24.0 or <24.0), Diabetes (Yes or No), Use of neoadjuvant radiotherapy (Yes or No), Tumor to anal verge (≥ 7 cm or <7 cm), Multiple high-risk factors (Yes or No), Pathological T stage (0-2 or 3-4), Pathological N stage (positive or negative), Presence of prior abdominal surgery (Yes or No), Center effect (High-volume centers ≥ 50 cases versus low-volume centers <50 cases) . For subgroup analyses, between-group differences and corresponding 97.5% CIs will also be presented. The RRs will be reported with corresponding 95% CIs (see appendix Table 3).

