4.8 Sensitivity analysis

Sensitivity analyses will be conducted for the PP and AT populations. Sensitivity models will replicate the primary analysis to ensure consistency across populations. The statistical methods used in these sensitivity analyses will be consistent with those applied to the ITT population. Results will be compared and interpreted across the ITT, PP, AT populations to determine whether protocol violations or missing data have an impact on the study outcomes.

5. Safety monitoring

Safety indicators will be monitored and analyzed in the safety population. Each participating medical center will designate independent monitors to oversee safety indicators, including the postoperative severe complication rate and serious adverse events.

To ensure participant safety and trial rigor, an independent DSMB was composed of a colorectal surgeon, a biostatistician, and an ethics consultant. The DSMB conducted blinded reviews (with no access to group allocation) of the primary outcome: the incidence of 90-day severe complications (Clavien-Dindo grade \geq III) and all serious adverse events (SAEs) every 6 months. During these reviews, no protocol violations or safety signals

warranting trial suspension were identified, and the DSMB consistently recommended that the trial continue as planned.

6. Appendix tables

Table 1

Characteristics	Stent-based Diverting Technique (n=)	Ileostomy (n=)
Age, y		
Mean ± SD	XX ± XX	XX ± XX
Group, No. (%)		
< 60	XX (XX)	XX (XX)
≥60	XX (XX)	XX (XX)
Gender, No. (%)		
Male	XX (XX)	XX (XX)
Female	XX (XX)	XX (XX)
Body mass index*		
Mean ± SD, kg/m2	XX (XX)	XX (XX)
Group, No. (%)		
<18.5 (Underweight)	XX (XX)	XX (XX)
18.5-23.9 (Normal)	XX (XX)	XX (XX)
≥24.0 (Overweight/Obese)	XX (XX)	XX (XX)
Smoking	XX (XX)	XX (XX)
Drinking	XX (XX)	XX (XX)
Concomitant, No. (%)		
Hypertension	XX (XX)	XX (XX)
Diabetes	XX (XX)	XX (XX)
Cardiovascular system diseases	XX (XX)	XX (XX)
Respiratory system diseases	XX (XX)	XX (XX)
Urinary system diseases	XX (XX)	XX (XX)

ASA classification, No. (%)†		
I (Healthy)	XX (XX)	XX (XX)
II (Mild systemic disease)	XX (XX)	XX (XX)
III (Severe systemic disease)	XX (XX)	XX (XX)
Eastern cooperative oncology group score		
0	XX (XX)	XX (XX)
1	XX (XX)	XX (XX)
Prior abdominal surgery, No. (%)	XX (XX)	XX (XX)
High-risk factors of anastomosis leakage, No. (%)		
Neoadjuvant radiotherapy	XX (XX)	XX (XX)
Tumor to anal verge≤7cm	XX (XX)	XX (XX)
Intraoperative factors‡	XX (XX)	XX (XX)
Others§	XX (XX)	XX (XX)

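### The primary risk difference is specified without covariates and no adjusted version is planned, so modest precision is given up although prognostic pre-randomisation variables are already collected

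*SAP*

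**What the plan says.** SAP section 4.6 (version 1.2) makes the non-inferiority test "based on the risk difference (RD) with a predefined non-inferiority margin of 2.8" percent and gives the estimator in one sentence: "The RD and its 97.5% one-sided confidence interval will be estimated using binomial regression with identity link". No covariate, stratum or centre term follows. The word unadjusted does not appear either, but a treatment-only model is the natural reading. Section 4.8 reruns the same model in the per-protocol and as-treated populations, so no adjusted RD is planned anywhere.

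The variables that could be used are already in the plan. Appendix Table 1 has a block labelled "High-risk factors of anastomosis leakage, No" that includes neoadjuvant radiotherapy and tumour height, and it also lists sex, BMI and diabetes. Section 4.6 uses these only to define subgroups. Centre appears only as a volume class: "Center effect (High-volume centers ≥ 50 cases versus low-volume centers <50 cases".

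Section 4.3 says: "For missing baseline data (age, BMI, etc.), multiple imputation by chained equations (MICE) will be used". It does not say which analyses the imputed datasets feed.

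**The concern.** The non-inferiority verdict depends on whether one upper confidence limit lies below 2.8 points. Part of the random error in that limit comes from chance differences between arms in factors that predict severe complications. Where such factors are measured before randomisation, a prespecified adjusted estimate of the same RD removes part of that error without changing the estimand, the margin or alpha. The plan does not take this gain.

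There is also a specification issue. In an open-label trial, a model given only by its link leaves it open whether covariates enter, and the imputation of baseline data invites the question of which model was meant to use it.

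**Working it through.** **Inputs from the SAP.** Control rate 14% and margin 2.8 points (section 4.6), one-sided alpha 0.025 (section 4.2), allocation 1:1 (section 1). The margin reproduces exactly: 0.14 × 0.20 = 0.028. One-sided 0.025 gives z = 1.96, which matches the one-sided 97.5% limit.

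**Inputs the SAP does not give.** Arm size, expected SDT rate, factor prevalence and factor effects. All values of these below are assumptions.

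**Step 1: range of arm sizes.** For 80% power, n per arm = (1.96 + 0.842)² × [0.14 × 0.86 + p(1 − p)] / (0.028 + 0.14 − p)², where p is the SDT rate.
- p = 14%: 7.85 × 0.2408 / 0.000784, about 2,411
- p = 12%: 7.85 × 0.2260 / 0.002304, about 770
- p = 10%: 7.85 × 0.2104 / 0.004624, about 358
- p = 8%: 7.85 × 0.1940 / 0.007744, about 197

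**Step 2: is the unadjusted test valid?** Trials were simulated (40,000 per setting) with a 14% control rate and three binary factors of prevalence 40%, 50% and 30%. Odds ratios were 2/2/1.5 (factors explain about 3% of outcome variance) or 3/3/2 (about 8%). The adjusted analysis was a Mantel-Haenszel stratified RD. With a true RD of 2.8 points, non-inferiority was declared in 2.5% to 2.8% of trials unadjusted and 2.5% to 2.7% adjusted. Mean bias of the unadjusted RD was zero within simulation error.

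**Step 3: how far does chance imbalance move the RD?** For one binary factor with prevalence q and risk contrast d, SD of the shift = d × √(2q(1 − q)/n). With q = 0.5 and odds ratio 2 the risks are about 9.9% and 18.1%, so d = 0.082.
- n = 200: 0.082 × √(0.5/200) = 0.41 points; 0.41/2.8 = 15% of the margin
- n = 2,411: 0.082 × √(0.5/2,411) = 0.12 points; 4% of the margin

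For three factors, from the simulation:

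| Per arm | OR 2/2/1.5: SD, share of margin | OR 3/3/2: SD, share of margin |
|---|---|---|
| 150 | 0.73 points, 26% | 1.15 points, 41% |
| 200 | 0.63, 22% | 0.99, 35% |
| 500 | 0.40, 14% | 0.63, 22% |
| 2,411 | 0.18, 6% | 0.29, 10% |

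The full range is therefore about 4% to 40%. For scale, the half-width 1.96 × √(2 × 0.14 × 0.86/n) is 6.8 points at 200 per arm, 4.3 at 500 and 1.96 at 2,411.

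**Step 4: what does adjustment gain?** Power at a true RD of zero, unadjusted to adjusted:

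| Per arm | OR 2/2/1.5 | OR 3/3/2 |
|---|---|---|
| 150 | 10.8% to 10.3% | 10.6% to 10.4% |
| 200 | 12.8% to 12.6% | 12.7% to 13.0% |
| 500 | 24.8% to 25.5% | 25.1% to 26.6% |
| 2,411 | 80.1% to 81.4% | 79.7% to 83.0% |

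A separate simulation of logistic regression with standardisation, at an assumed 300 per arm and five covariates, cut the variance of the RD by 2.2%, 4.5% and 9.6% at covariate AUCs of 0.62, 0.69 and 0.75.

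**Step 5: effect on the upper limit.** At 300 per arm the SE is √(2 × 0.14 × 0.86/300) = 2.83 points and the half-width 1.96 × 2.83 = 5.55. Those variance cuts narrow it by 5.55 × (1 − √(1 − 0.022)) = 0.06, 5.55 × (1 − √(1 − 0.045)) = 0.13 and 5.55 × (1 − √(1 − 0.096)) = 0.27 points, which is 2% to 10% of the margin.

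**Step 6: does the choice change verdicts?** At the arm sizes that give about 80% power (358, 770, 2,411), the standardised and unadjusted analyses disagreed on non-inferiority in 4.6%, 3.5% and 4.3% of simulated trials with the weaker factors, and in 6.7%, 7.5% and 7.4% with the stronger ones.

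**The case against.** The strongest reply is that an unadjusted RD in a randomised trial is a sound and transparent primary analysis, and that preferring adjustment is a matter of taste. Much of this stands. A reader might infer that chance imbalance biases the result; it does not, because it is part of the sampling error that the interval already covers (step 2).

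A reader might also infer that imbalance moves the estimate by a large part of the margin. The SAP has no sample size, prevalence or prognostic effect from which to derive that. The shift is also not a separate harm from the small variance gain. For an efficient adjusted estimator, Var(unadjusted − adjusted) is about Var(unadjusted) − Var(adjusted). At 300 per arm this gives 2.83 × √0.022 = 0.42, 2.83 × √0.045 = 0.60 and 2.83 × √0.096 = 0.88 points, close to the 0.51, 0.74 and 0.97 simulated. It is the 2% to 10% gain expressed as a square root.

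A third tempting inference is that the imputation in section 4.3 has no use. The subgroup analyses in section 4.6 and the interaction column of the appendix subgroup table rely on baseline variables, so it may serve there; the SAP simply does not say. Nor can the plan be faulted for ignoring stratification factors, since randomisation details may be in the protocol, which is not at hand.

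Finally, choosing covariates late adds discretion. The trial is open label, and version 1.2 describes follow-up and DSMB reviews in the past tense, although section 4.1 places the analysis after database lock. This is a fair limit on the remedy, and the fix below is conditional for that reason. It does not remove the point: the two analyses can disagree (step 6), which is a reason to write down which one is primary.

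**Conclusion.** The point holds as a modest, avoidable loss of precision together with an under-specified model. It is not an invalid test. Under the assumed strengths, adjustment lowers the variance of the RD by about 2% to 10%. Power changes by between nothing and about 3 points; with the smallest arms the stratified analysis showed no gain or a loss of up to half a point. The error rate at the margin is near 2.5% with either analysis. A typical difference between the two estimates is about 4% to 40% of the margin, at the low end with large arms and weak factors and at the high end with about 150 per arm and strong factors. These figures rest on assumed arm sizes, prevalences, odds ratios and AUCs; only the 14% rate, the 2.8-point margin, alpha and the 1:1 ratio come from the SAP. The change is worth making because it is cheap and leaves the estimand, margin and alpha as they are.

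**What to change.** Keep the RD, the 2.8% margin and one-sided alpha 0.025. Before outcomes are seen by arm, amend section 4.6 as follows.
- Fix a short covariate list known before randomisation: neoadjuvant radiotherapy, tumour-to-anal-verge distance, sex, BMI and diabetes, plus any factor used to stratify randomisation. Exclude pathological T and N stage, which are known only after surgery. Because randomisation was intraoperative, leave out intraoperative factors unless they are recorded before allocation.
- Fit a logistic model with treatment and these covariates, and obtain the marginal RD and its one-sided 97.5% limit by standardisation, with a delta-method or bootstrap standard error. Identity-link models with several covariates may fail to converge.
- Use the MICE datasets for missing covariates, and state in section 4.3 which analyses they feed.
- Report the unadjusted identity-link RD as a sensitivity analysis.

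If outcomes by arm have already been seen, keep the unadjusted RD as primary, say explicitly that it is unadjusted, and report the adjusted RD as supportive.

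Cost: SAP wording and some extra programming, including combining imputation with standardisation; no new data. The list must be short, since an assumed 300 per arm at 14% yields only 600 × 0.14 = 84 events, and it must be locked in advance.
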